### 1.1 Treatment of methamphetamine use disorder and management of HIV

Use of MA is disproportionately higher among men who have sex with men (MSM) than the general U.S. population (5.9% in HIV-negative MSM and 12.3% in HIV-positive MSM) (1, 2). Chronic MA use is linked to myriad health conditions including psychiatric disorders, cardiovascular disease, social problems, and infectious diseases such as HIV (25). MA use reduces adherence to antiretroviral therapy (ART) and engagement in HIV care (3, 4), and induces immune dysfunction (5). All of these factors can hamper people living with HIV (PLWH) from achieving and sustaining viral suppression, which contributes to forward HIV transmission. Reducing MA use is essential to managing HIV, reducing transmission, and maintaining health in PLWH with MA use disorder (MUD).

There are no effective pharmacological treatments in place for MUD (40). The most robust treatments use behavioral approaches (41-43). Research in substance use intervention has demonstrated that contingency management (CM), which provides incentives that escalate in value for provision of consecutive biomarkers demonstrating drug abstinence, is an effective positive reinforcement approach to promoting abstinence from MA and other substances (6, 43-49). CM is based on the theory that MUD or other substance disorder is due to sustained, high-value drug reinforcement and that providing incentives that compete with drug reinforcement can successfully alter drug taking and produce sustained drug abstinence (15).

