in CTRA expression in HIV-negative MSM who experienced homophobic victimization (Figure 1) (10), a problem also comorbid with MA use in MSM (34). The CTRA has also been shown to be related to the development of depressive and

Table 1. CTRA gene expression and transcription factor activation in response to stress vs. well-being

Stress response	Well-being response	Transcription factor	Genes expressed
↑	↓	CREB, NF-κB, AP-1	Inflammatory: IL1A, IL1B, IL6, IL8, TNF, PTGS1, PTGS2, FOS, FOSB, FOSL1, FOSL2, JUN, JUNB, JUND, NFKB1, NFKB2, REL, RELA, and RELB
↓	↑	IRF	Interferon: GBP1, IFI16, IFI27, IFI27L1-2, IFI30, IFI35, IFI44, IFI44L, IFI6, IFIH1, IFIT1-3, IFIT5, IFIT1L, IFITM1-3, IFITM4P, IFITM5, IFNB1, IRF2, IRF7-8, MX1-2, OAS1-3, and OASL Antibody synthesis: IGH, IGLL1, and IGLL3

anxiety-related disorders (18-22), which are highly comorbid with MA use (23-25). Research on compulsive gaming also may suggest that CTRA is linked to addictive behaviors and dynamics (16). Participants who experienced internet gaming as compulsive

, isolating, or dissatisfying had increases in their CTRA gene expression, while those who felt accomplishment and connectedness with online gamers had low CTRA levels (16).

The CTRA also involves some of same gene regulatory pathways that contribute to MA-related pathogenesis, such as those involving inflammation and innate antiviral responses (particularly relevant to PLWH). Chronic MA use in pre-clinical experiments and stimulation of inflammation using lipopolysaccharide (LPS) was shown to induce anxiety-like and sickness behaviors in adult rats, while neonatal exposure to LPS-induced inflammation was linked to behavioral sensitization to MA self-administration during adulthood (23, 24, 61, 62). Chronic MA use is also associated with increased CREB, AP-1, and NF-κB activation, transcription factors driving CTRA gene expression and likely involved in MA-induced inflammation (8, 28-31). The CTRA has also been epidemiologically linked to inflammatory health problems such as cardiovascular disease (26, 27), a common cause of mortality in people with MUD (63, 64).

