Both chronic MA use and comorbid psychosocial problems such as HIV stigma and depression have been linked to the progression of HIV (65-67). One explanation for this may be their impact on poorer ART adherence (68), while another possibility is the mediating role of inflammation and/or impaired antiviral response on viremia (67, 69-73). Prior research has demonstrated that greater cytokine levels and activation of CTRA-related transcription factors such as NF-κB and CREB induce replication of HIV and predict increases in viral load (30, 74-77). Conversely, HIV itself induces chronic inflammation and enhances risk of inflammatory-related health conditions such as cardiovascular disease (78-80) and depression (81). Risk of these inflammatory conditions in PLWH is further exacerbated by comorbid MA use (69, 70).

For these reasons, measuring inflammatory patterns in CTRA may have clinical relevance to management of HIV and related chronic conditions in the context of MA treatment.

However, the impact of IFN-I activity on HIV disease progression is less clear (82, 83). While IFN-I responses to acute HIV are involved in initial reduction of the virus (71, 72), prolonged IFN-1 activation can lead to immune dysregulation and T-cell exhaustion, and in turn, increased viral load (82, 83). As stated previously, CTRA gene expression involves threat/stress-induced increases in inflammatory gene expression and decreases in IFN-1 and antibody gene expression, all of which are markers linked to HIV viral load. Whether physiologic patterns of IFN gene expression underlie the link between psychosocial health and the body's management of HIV warrants investigation.

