**10 EVALUATIONS BY VISIT**

Below is the schedule of study elements by study arm (i.e., contingency management group vs. non-substance using control (Table 3). Both groups have a screening and baseline visit.

Table 3. Schedule of study elements by study arm

Element	Visit																		
	S	B	1.1	1.2	2.1	2.2	3.1	3.2	4.1	4.2	5.1	5.2	6.1	6.2	7.1	7.2	8.1	8.2	12.0
SCID-5	▲◇																		
Screening survey and locator form	▲◇																		
Urine drug test (MA, AMP, opioids, MDMA, cannabis)	▲◇	▲◇	▲	▲	▲	▲	▲	▲	▲	▲◇	▲	▲	▲	▲	▲	▲	▲	▲◇	▲◇
Record/review HIV medications	▲◇	▲◇								▲◇								▲◇	▲◇
HIV rapid test or certification	▲◇																		
Contingent Rewards			▲	▲	▲	▲	▲	▲	▲	▲	▲	▲	▲	▲	▲	▲	▲	▲	▲
Plasma (for Viral load)		▲◇								▲◇								▲◇	▲◇
PBMC (for transcriptome profiling)		▲◇								▲◇								▲◇	▲◇

Serum (for COVID-19 immunoassay)		▲◇																	▲◇	
Behavioral survey		▲◇							▲◇										▲◇	▲◇
▲ = Contingency management (CM) for HIV-positive MSM with METH use disorder. ◇ = Non-substance-using control of HIV-positive MSM.																				

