### 15.6 Multivariate Analysis for Associations Between Endpoints

Associations between MA use, CTRA gene expression, and viral suppression. All models in Aim 1 will adjust for age, race, education, employment, housing, and mRNA encoding markers of major leukocyte subsets (e.g., CD4). We will also assess for confounding by COVID-19 infection detected by immunoassay, liver function, and type of ART prescription. MA use and CTRA. Using a linear mixed effects regression, we will test whether a negative MA urine test is associated with reductions in CTRA contrast scores across four time points—Visits B, 4.2, 8.2, and 12.0. We will use a time (days) by MA urine result interaction term to estimate difference in change in CTRA as

a function of MA test result. CTRA and viral load. Using a mixed effects logistic regression, we will test whether CTRA gene expression is associated with viral suppression (<200c/mL) across three time points—Visits B, 4.2, 8.2, and 12.0. We will include a time (days) by CTRA gene expression interaction term to test this association longitudinally. We will also test whether CTRA and viral load are reciprocally associated using dynamic panel data modeling with maximum likelihood (102-104). This approach will allow us to simultaneously test whether CTRA is associated with viral load at subsequent observations, and account for whether CTRA is affected by prior values of viral load (102-104).

**Associations between psychosocial indicators of substance use severity and CTRA.** Using a linear mixed effects regression, I will test whether the seven domains of the Addiction Severity Index (ASI) is associated with reductions in CTRA contrast scores across four time points—Visits B, 4.2, 8.2, and 12.0. I will use a time (days) by ASI domain score interaction term to estimate change in CTRA as a function of changes in ASI scoring. We will control for age, race, education, and mRNA markers of major leukocyte subsets.

**Indirect associations between MA use, CTRA, and viral suppression.** I will use propensity scores to test the degree to which CTRA mediates the association between MA use and viral suppression (105, 106). The general theory is that we would compute propensity score for CTRA—the probability of having a particular CTRA level—to compare participants who used MA with those who would have had the same value of the CTRA had they used MA.

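### The model of viral suppression on CTRA leaves out methamphetamine use, which the protocol itself links to both

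*Combined protocol and SAP*

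**What the plan says.** Section 15.6 gives one adjustment set for the first aim: "All models in Aim 1 will adjust for age, race, education, employment, housing, and mRNA encoding markers of major leukocyte subsets (e.g., CD4". It adds a second tier: "We will also assess for confounding by COVID-19 infection detected by immunoassay, liver function, and type of ART prescription". In the model at issue, "we will test whether CTRA gene expression is associated with viral suppression (<200c/mL" is the question, and the terms added are CTRA, time and their interaction. A dynamic panel model then examines CTRA and viral load in both directions. MA use, study group and ART adherence are listed for neither model. The suppression model also appears in the synopsis under Primary Analysis Plan, and Section 3.1 puts viral load in the primary objective.

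The background supplies the links. Section 1.1: "MA use reduces adherence to antiretroviral therapy (ART) and engagement in HIV care". Section 1.2, on CTRA: "Chronic MA use is also associated with increased CREB, AP-1, and NF-κB activation". Section 1.2, on HIV progression in people who use MA or have comorbid psychosocial problems: "One explanation for this may be their impact on poorer ART adherence (68), while another possibility is the mediating role of inflammation".

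On data, Table 3 in Section 10 schedules a urine drug test, blood for CTRA and viral load, a behavioral survey and "Record/review HIV medications" at Visits B, 4.2, 8.2 and 12.0, in both groups.

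**The concern.** On the protocol's own account, MA use sits upstream of both sides of this regression. It is expected to raise CTRA, and it is expected to lower viral suppression by a route that need not pass through CTRA. Leaving it out gives the CTRA coefficient the combined effect of those two links, even if CTRA has no relation to HIV control.

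The design sharpens this. Thirty-five men with MA use disorder are pooled with 20 controls selected for no substance use, so MA status differs strongly between groups as well as within treated men over time. A participant random intercept removes neither source of variation. At stake is the claim in Section 1.2 that CTRA may matter clinically for managing HIV. Without MA use in the model, that explanation cannot be separated from the rival one that the same section names.

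**Working it through.** **1. The plan's own figures.** 55 × 4 = 220 and 220 × 0.80 = 176, as stated in Section 15.7. The 154 observations for the logistic model come with power 0.80, CTRA SD 1.44 and odds ratio 1.5; alpha and the proportion suppressed (p) are not given. The usual formula, assuming two-sided alpha 0.05 and an odds ratio per CTRA unit, is

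n = (1.960 + 0.842)² / [p(1 − p) × (ln 1.5 × 1.44)²] = 7.849 / [0.3409 × p(1 − p)].

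This gives 92 at p = 0.50, 110 at 0.70, 144 at 0.80, 154 at 0.817 and 181 at 0.85. So 154 fits p of about 0.82 with no allowance for covariates, or a lower p with an unstated one (R² = 0.40 at p = 0.50). It cannot be reproduced from the stated inputs alone.

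**2. The paths, side by side.**
- MA use to CTRA: Section 1.2 (transcription factor activation).
- MA use to viraemia, not through CTRA: Sections 1.1 and 1.2 (adherence).
- CTRA to viraemia: the association under test.
- Conditioning on MA use: not listed in Section 15.6.

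**3. Bias when CTRA has no effect.** None of these inputs is in the documents except the SD: 30% or 40% of visits MA-positive; suppression 60% or 70% when positive and 85% or 90% when negative; CTRA shifted by 0.3, 0.5 or 0.8 SD with MA use (SD 1.44); suppression independent of CTRA given MA use. Pooled logistic regression on centred CTRA alone gives these odds ratios of non-suppression per CTRA unit:
- pairings 60/85% and 70/90%: 1.06 to 1.17;
- all combinations, adding 60/90% and 70/85%: 1.04 to 1.23.

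On the log scale, ln 1.04 / ln 1.5 = 0.10 and ln 1.23 / ln 1.5 = 0.51, so the bias is about 10-50% of the planned effect. With MA use in the model the odds ratio returns to about 1.00.

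**4. The same at trial size.** Assumed: 35 and 20 participants, four visits, MA-positive in 95% of the treated group at baseline and 50% later (overall 35/55 × (0.95 + 3 × 0.50)/4 = 39%), suppression 90% without MA, no CTRA effect, GEE, 600 runs per row. Odds ratios here are for suppression, so bias shows as values below 1. Monte Carlo error near 5% is √(0.05 × 0.95/600) = 0.9 points.

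| CTRA shift (SD) | Suppression with MA | OR without MA term | False positives | OR with MA term | False positives |
|---|---|---|---|---|---|
| 0.3 | 80% | 0.955 | 8.0% | 0.996 | 5.7% |
| 0.3 | 70% | 0.936 | 10.2% | 0.997 | 7.2% |
| 0.3 | 60% | 0.910 | 12.0% | 0.995 | 6.0% |
| 0.5 | 80% | 0.928 | 8.8% | 0.993 | 5.8% |
| 0.5 | 70% | 0.902 | 12.8% | 1.010 | 5.7% |
| 0.5 | 60% | 0.862 | 28.0% | 0.994 | 5.5% |
| 0.8 | 80% | 0.913 | 11.7% | 1.009 | 6.2% |
| 0.8 | 70% | 0.856 | 28.3% | 1.010 | 9.3% |
| 0.8 | 60% | 0.810 | 46.7% | 1.000 | 5.8% |

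**5. Cost of the extra term.** The requirement becomes 154/(1 − R²), where R² is the share of CTRA variance that MA use explains. With shift d (in SD) and MA-positive fraction m, R² = d²m(1 − m)/[1 + d²m(1 − m)].
- d = 0.3, m = 0.3: 0.0189/1.0189 = 0.019, so 154/0.981 = 157.
- d = 0.8, m = 0.4: 0.1536/1.1536 = 0.133, so 154/0.867 = 178.

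The 176 observations suffice up to R² = 1 − 154/176 = 0.125. Clustering of visits within participants is ignored throughout this step.

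**The case against.** **The size is assumed, and the model is simplified.** This stands. The documents give no suppression rate by MA status and no CTRA shift. The calculations omit the time terms, the random intercept and the listed covariates, some of which may absorb part of the bias. In the mildest row the false-positive rate is 8.0%, inside the 5.5-9.3% seen across settings after adjustment. The 46.7% needs the strongest value of both links.

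**The plan claims only association, in a pilot.** True, so the documents do not support saying that the result would necessarily be presented as an effect of CTRA on HIV control. But an association explained by a measured common cause says little about CTRA, and the test belongs to the primary objective.

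**Other parts of the plan cover it.** The panel model addresses direction, not a common cause. Type of ART is a regimen, not whether it was taken. The mediation analysis uses MA use as the exposure, but it is separate and exploratory and does not adjust this test. Section 15 says a detailed SAP will follow; that is an opening to correct the list, not a correction.

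**Two stronger readings go too far.** A reader might infer that adherence is unmeasured. Section 9.1.1 records dose, frequency and dates of medication, and the survey items are not listed, so the documents show only that no adherence measure is named. A reader might also infer that the mediation analysis shares the flaw. MA use is already in it, and a parallel path through adherence belongs to the direct effect. That path does not by itself bias the path through CTRA.

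**Conclusion.** The omission is in the text, and the reason it matters is the protocol's own. As specified, the CTRA-viral suppression model, and the panel model as described, cannot separate CTRA from MA use. Under the assumed ranges, the spurious odds ratio of non-suppression is about 1.04-1.23 per CTRA unit, or 10-50% of the planned log odds ratio, and adjusting for MA use brings it back to about 1.00. These figures illustrate the problem; they do not predict this trial's result. If MA use shifts either CTRA or suppression only weakly, the bias is small. The point concerns MA use. It does not establish that adherence goes unrecorded or that the mediation analysis is confounded in the same way, and the calculations give no separate support for adding adherence as a model term.

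**What to change.** In Section 15.6, the synopsis and the SAP still to be written:

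1. Add the visit's MA urine result to the CTRA-viral suppression model, and add it as a time-varying covariate to the panel model.
2. Report the CTRA estimate with and without that term, and describe it as an association.
3. State whether adherence is captured by the medication record or the behavioral survey. If it is, use it in a sensitivity analysis; if not, name it as a limitation.
4. State the alpha, suppression proportion and covariate allowance behind the 154 observations.

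Items 1 and 2 need wording only, because the urine results are already collected at Visits B, 4.2, 8.2 and 12.0. The price is one more term in a small sample and some precision. If MA use explains 2-13% of CTRA variance, the requirement is about 157-178 observations, so the 176 at 80% retention covers all but the top of that range, before any allowance for clustering.

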**PROTOCOL SYNOPSIS**

TITLE	Expression of stress markers in MSM living with HIV receiving contingency management for methamphetamine use disorder (a.k.a. “EXPRESS+”)
SPONSOR	[name], MPH
FUNDING ORGANIZATION	
NUMBER OF SITES	1
RATIONALE	Determining whether a patient is both feeling better and improving physiologically when treating people living with HIV (PLWH) for methamphetamine use disorder requires identification of a clinically significant measure separate from abstinence. This study will to address this challenge by testing a gene expression (mRNA) pattern identified by the field of social genomics, which may provide insight into both psychosocial health and biological processes that impact chronic disease risk in PLWH receiving MUD treatment.
STUDY DESIGN	This is a within-subjects, two-arm clinical trial with 35 HIV-positive MSM receiving contingency management for treatment of methamphetamine use disorder and 20 HIV-positive MSM serving as a non-substance-using healthy control (N=55 total).
PRIMARY OBJECTIVE	To investigate whether differences in CTRA expression (mRNA) coincide with differences in methamphetamine use and viral load over the course of 12 weeks in HIV-positive MSM with and without methamphetamine use disorder.

SECONDARY OBJECTIVES
	
 
• To investigate whether differences in seven psychosocial dimensions of drug addiction (Short Inventory of Problems Revised (SIP-R))—physical, social, intrapersonal, interpersonal, impulse control—are associated with differences in CTRA gene expression.
 
• To conduct an exploratory pilot investigation to determine the degree to which CTRA mediates the association between METH use and viral suppression.
 

NUMBER OF SUBJECTS
	55

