Primary Analysis Plan	Using a linear mixed effects regression, we will test whether a negative MA urine test is associated with reductions in CTRA contrast scores across four time points—Visits B, 4.2 (Week 4), 8.2 (Week 8), and 12.0 (Week 12 follow-up). We will use a time (days) by MA urine result interaction term to estimate difference in change in CTRA as a function of MA test result. Using a mixed effects logistic regression, we will test whether CTRA expression is associated with viral suppression (<200c/mL) across three time points— Visits B, 4.2 (Week 4), 8.2 (Week 8), and 12.0 (Week 12 follow-up). We will include a time (days) by CTRA expression interaction term to test this association longitudinally.
Rationale for Number of Subjects	Power analysis for this pilot study indicates that a minimum of 135 person-observations will be sufficient to test whether MA use or the psychosocial Short Inventory of Problems (SIP-R) are associated with CTRA expression, assuming a medium effect size of 0.15 and power level of .80. Additionally, a logistic model testing whether CTRA is associated with viral suppression would require a minimum of 154 person-observations, assuming a power level of .80, a CTRA standard deviation of 1.44, mean centering of CTRA, and an odds ratio of 1.5. When modeling viral load as a continuous outcome, 135 person-observations is the minimum to test whether CTRA is associated with viral load (c/mL), assuming a medium effect size of 0.15 and power level of .80. These analyses will include 55 participants over four measurements of CTRA, for a total of 220 person-observations (176 person-observations at 80% retention), which is sufficient for these thresholds.

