### 3 STUDY OBJECTIVES

#### 3.1 Primary Objective

To investigate whether changes in CTRA gene expression coincide with changes in MA use and viral load over the course of 12 weeks in HIV-positive MSM with and without MUD.

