### 4 STUDY DESIGN

#### 4.1 Study Overview

The proposed study will be a two-arm clinical trial design of 55 MSM living with HIV, of whom 35 HIV-positive MSM with MUD (MA+/HIV+) will receive contingency management for MA reduction, and 20 HIV-positive, non-substance-using MSM (MA-/HIV+) will participate as a control. There is extensive evidence that CM has greater efficacy than a non-contingent condition in the treatment of MUD (41-44, 46-49, 88), so it may raise ethical concerns to withhold CM from people with MUD who are willing to receive treatment. For this reason, this study uses a control of non-substance using HIV-positive (MA-/HIV+) MSM rather than a non-contingent yoked control of HIV-positive MSM with MUD (89). The use of a non-substance-using HIV-positive control will provide a baseline level of CTRA among HIV-positive MSM who do not have MUD or use other substances, which can be compared against CTRA levels in those with MUD. Screening data will be reviewed to determine subject eligibility. Subjects who meet all inclusion criteria and none of the exclusion criteria will be entered into the study. The following treatment regimens will be used:

- Contingency management twice weekly for 8 weeks, with post-treatment follow-up at Week 12.

- Non-substance-using control will not receive a treatment, but will be evaluated at Baseline, Weeks 4, 8, and 12.

The total duration of subject participation will be 14 weeks. The total duration of the study is expected to be 4 years: 1 year of rolling subject recruitment, 1 year for final subject follow-up, 1 year of biospecimen processing, and 1 year of analysis.

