## 15.7 Sample Size and Randomization

This study will enroll 55 participants, who will be evaluated for the course of 14 weeks, including screening. Power analysis for this pilot study indicates that a minimum of 135 person-observations will be sufficient to test whether MA use or the psychosocial Addiction Severity Index (ASI) are associated with CTRA gene expression, assuming a medium effect size of 0.15 and power level of .80. Additionally, a logistic model testing whether CTRA is associated with viral suppression would require a minimum of 154 person-observations, assuming a power level of .80, a CTRA standard deviation of 1.44, mean centering of CTRA, and an odds ratio of 1.5. When modeling viral load as a continuous outcome, 135 person-observations is the minimum to test whether CTRA is associated with viral load (c/mL), assuming a medium effect size of 0.15 and power level of .80. These analyses will include 55 participants over four measurements of CTRA, for a total of 220 person-observations (176 person-observations at 80% retention), which is sufficient for these thresholds.

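### The pooled urine-CTRA model omits arm and arm-by-time, and its named interaction cannot detect a constant abstinence effect

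*Combined protocol and SAP*

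**What the plan says.** Section 15.6, repeated as the Primary Analysis Plan in the synopsis, specifies a linear mixed model: "we will test whether a negative MA urine test is associated with reductions in CTRA contrast scores across four time points" (Baseline and Weeks 4, 8 and 12). It continues: "We will use a time (days) by MA urine result interaction term to estimate difference in change in CTRA as" a function of the test result. On covariates: "All models in Aim 1 will adjust for age, race, education, employment, housing, and mRNA encoding markers of major leukocyte subsets". COVID-19 infection, liver function and type of ART are to be assessed as confounders. Arm and arm-by-time are in neither list.

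Section 15.7 says "These analyses will include 55 participants over four measurements of CTRA", so the 35 men with methamphetamine use disorder (MUD) and the 20 controls are pooled. Section 8.1 states that allocation is not randomized. Section 6.2 requires a recent positive MA test of the MUD men. Section 6.3 excludes controls who test positive for MA or report using it in the past 6 months.

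Arm does appear in Section 15.3, which compares CTRA trajectories between the two conditions but mentions no urine term. The plan does not say how that model relates to the one in 15.6. The objective in Section 3.1 is "To investigate whether changes in CTRA gene expression coincide with changes in MA use and viral load over the course of 12 weeks"; the synopsis has "To investigate whether differences in CTRA expression (mRNA) coincide with differences in methamphetamine use and viral load".

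**The concern.** Because of the entry criteria, urine result is partly a label for arm: positive results come essentially from MUD men, and many negative results come from controls. The plan gives its own reason to expect the arms to differ in CTRA level, since Section 1.2 links problems that accompany MA use to CTRA. The planned covariates may remove only part of this. For example, controls may not use tobacco or drink heavily, while MUD men may, short of another use disorder. Section 15.2 names smoking and heavy alcohol use as covariates, but the 15.6 list does not repeat them.

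A significant urine or time-by-urine term could therefore reflect the difference between men with and without MUD rather than abstinence. That matters for a study that asks whether CTRA can serve as a treatment endpoint. Separately, the stated test is whether a negative urine goes with lower CTRA, but the one urine coefficient named is an interaction with time. That is zero if abstinence lowers CTRA by a constant amount.

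**Working it through.** **1. The plan's own figure.** Section 15.7 says "a minimum of 135 person-observations will be sufficient to test whether MA use" or the psychosocial scale is related to CTRA, at effect size 0.15 and power 0.80. Reading 0.15 as f² and assuming alpha 0.05, an overall F test with 14 predictors and noncentrality 0.15 × N gives N = 135 (power 0.802); 13 predictors give 131 and 15 give 139. A test of one coefficient needs 55-56. The totals reproduce: 55 × 4 = 220 and 220 × 0.8 = 176. So 135 fits an overall test and does not show which urine coefficient was powered.

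**2. The models.** Let A = 1 for the MUD arm, N = 1 for a negative urine, and t = time.
- Planned: E[CTRA] = b0 + b1·t + b2·N + b3·t·N + covariates.
- No abstinence effect, but an arm gap g and an arm slope difference s: E[CTRA] = g·A + s·A·t + terms common to both arms. Omitting A loads g onto b2, and omitting A·t loads s onto b3. A and N are negatively correlated, so a relative rise in the MUD arm (s > 0) makes b3 negative, which looks like benefit; a relative fall makes it positive.
- Constant abstinence effect d: E[CTRA] = d·N + common terms, so b3 = 0.

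**3. How far urine stands in for arm.** Assume MUD-arm negative rates of 15/45/50/40% by visit (mean 37.5%) and controls always negative. MUD men then give 140 × 0.375 = 52.5 negative observations and controls 20 × 4 = 80. Controls supply 80 / 132.5 = 60% of the negatives and none of the positives.

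**4. Simulation inputs, all assumed.** 35 + 20 men; days 0/35/63/91; ICC 0.5; CTRA SD 1; 80% of visits observed at random; the rates in step 3; random-intercept REML; two-sided 5% tests; time zero at baseline. Covariates are not simulated, so gaps mean what remains after adjustment.

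**5. Results with no abstinence effect (ranges are over repeated runs).**

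| Arm difference | Planned urine term b2 | Planned time-by-urine b3 |
|---|---|---|
| None | about 5% | about 5% |
| Level gap 0.5 SD | 10-11% | about 5-7% |
| Level gap 0.8 SD | 18-21% | about 5-7% |
| Slope ±0.5 SD over 91 days | not tabulated | 19-23%; estimate about -0.36 or +0.36 |

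Over nine settings (ICC 0.3/0.5/0.7; 25/37/50% of MUD visits negative), the interaction rejects 6.2-10.4% for a slope difference of 0.2 SD and 12.7-40.5% for 0.5 SD. Arm alone is not enough: in a variant with rates 10/50/55/45% and all visits observed, it leaves the interaction at 25% for a slope difference of -0.5 SD. Adding arm and arm-by-time restores about 4-6%.

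**6. Why split urine result as well.** If person-level CTRA and urine propensity correlate 0.3 or 0.5 within the MUD arm, the arm-adjusted unsplit urine coefficient rejects 6.7-9.1% or 9.6-15.0%. The within-person term rejects 4.0-6.2% in those and the other no-effect scenarios. If individual slopes also vary (SD 0.5 or 0.8 over 91 days, correlated 0.5 with urine propensity), unsplit time-by-urine rejects 7-15% or 15-28% even with both arm terms, and a joint test containing it rejects 7-12% or 12-25%. The within-person term, fitted without the interaction, stays at 4-7%.

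**7. Power.** For a constant effect of -0.5 SD the planned interaction rejects about 5-7%, that is, it has no power. The lower-order urine term in the same model rejects 51-81% with time zero at baseline and 82-96% with time mean-centred, so that term depends on a choice the plan does not state.

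**The case against.** Several points on the other side stand.

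- The planned interaction is robust to a level gap, and a level gap is all that Section 1.2 supports. No passage predicts a slope difference unrelated to abstinence. The size of that bias is therefore unknown, although Section 15.3 treats arm trajectories as an open question.
- A reader might infer that the plan leaves its urine coefficient wholly open. It does not: it names time-by-urine and says what it estimates, which fits the word changes in Section 3.1. The fair criticism is that this term cannot see a constant shift.
- Pooling may be deliberate, since controls supply a CTRA level "which can be compared against CTRA levels in those with MUD" and the synopsis speaks of differences. But Section 15.3 already makes that comparison, so adjusting 15.6 for arm loses nothing the plan needs.
- A reader might quote much larger false-rejection rates, up to 62.4% at a 0.8 SD gap. Those belong to a model with no interaction, which the plan does not specify.
- A reader might infer that this must be settled before the interim. Section 15.5 uses the models described before it, namely 15.3 and 15.4; the urine-CTRA model comes after. The documents do not support that urgency.
- A reader might set the MUD arm's 112 observations against the stated minimum of 135. That is not like for like: 135 fits an overall 14-predictor test, and a one-coefficient test at f² = 0.15 has 98% power at 112, ignoring clustering.

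This is also a pilot, and Section 15 promises a detailed SAP before the final analysis. That is where the change belongs.

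**Conclusion.** The concern holds and should be fixed. The omission of both arm terms is plain in the text. Its consequence depends on arm differences that the documents do not quantify. At ICC 0.5 and the assumed urine rates, residual gaps of 0.5 and 0.8 SD raise false rejection of the planned lower-order urine term to about 10% and 20%, and a slope difference of 0.5 SD raises that of the interaction to about 20%, in either direction. A slope difference of 0.2 SD does little (6.2-10.4%). With no arm difference there is no inflation. That the interaction is blind to a constant abstinence effect follows from the model and needs no assumed arm difference.

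**What to change.** In Section 15.6 and the synopsis, before the final analysis:

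1. Add arm and arm-by-time to the urine-CTRA model.
2. Replace urine result by the person's mean over the CTRA visits analysed and the deviation from that mean: E[CTRA] = b0 + b1·t + b2·A + b3·A·t + bW·(N - mean N) + bB·(mean N) + covariates. Name bW, fitted without an unsplit time-by-urine term, as the contrast that answers Section 3.1.
3. If time-by-urine is also reported, keep both arm terms, state time zero and treat it as supportive; or build it from the within-person part and allow random slopes.
4. State that the between-arm comparison belongs to Section 15.3.
5. In Section 15.7, state that the within-person effect rests mainly on the MUD arm: 35 × 4 = 140 observations, or 140 × 0.8 = 112 at 80% retention. Under the assumed rates only 42-59% of MUD men (15-21 of 35) have both a negative and a positive result among these visits.

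No new data are needed. The cost is power. For a constant -0.5 SD effect at ICC 0.5 and 25/37/50% negative, the pooled unadjusted urine effect has 85/87/87%, partly from the confounded between-arm contrast, and the within-person term 60/70/72%. If the effect instead grows from 0 to -1.0 SD by day 91, the within-person term has 74/79/76%, so it does not depend on the effect being constant.
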